### **3.5 Randomization Procedures**

Randomization is immediately after enrollment, stratified by study site, and completed via computer-generated random allocation with a block size of 6 by using the REDcap database. Understandably, neither the patient, caregiver, nor surgeon can be blinded to intervention allocation. However, the principal investigator (PI) and analysis team are blinded to participant randomization and the research team acquiring outcome data, whenever possible, is blinded to participant randomization.

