### 10.1.4 Measurement Time Points

The outcome of quality of life will be assessed at baseline during enrollment, one week after surgery, one month after surgery, 3 months after surgery, and 6 months after surgery. Participants will have a window of +/- 7 days to complete the surveys for each timepoint before it is considered “missed.”

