### 10.2.4 Measurement Time Points

The secondary outcome will be assessed at baseline during enrollment, one week after surgery, one month after surgery, 3 months after surgery, and 6 months after surgery. Participants will have a window of +/- 7 days to complete the surveys for each timepoint before it is considered “missed.”

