### 12.1.1 Randomization

Randomization occurs immediately after enrollment. Participants are stratified by study site. Using the REDCap database, group assignment (intervention or control) is determined via a computer-generated random allocation with a block size of 6. Patients, caregivers, and surgeons cannot be blinded to group assignment due to practical considerations; however, the principal investigator and analysis team are blinded to participant randomization. The research team collecting outcome data are blinded to participant randomization, whenever possible.

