### 12.4.1 Analysis Population

Our study will use an intent-to-treat approach in which all data from study patients in both intervention and control arms are used, regardless of the level of adherence to the study arm.

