### 12.4.2. Analysis Plan

The effect of group assignment (intervention or control) on the quality of life will be tested. Differences in outcomes between two arms at each visit will be tested by the two-sample t-test/Mann-Whitney test or Fisher's exact test/chi-squared test based on the data types of the outcomes. The effect of intervention on the quality of life after accounting for various confounding variable will be determined using a linear mixed model that accounts for within-subject variations due to repeated measures. Sensitivity analyses will assess whether there are differential effects on contingent on patient or study site characteristics on the primary outcomes.

The overall level of statistical significance was set at  $p<0.05$ . For all models, the research team will identify possible confounding variables for model adjustment, including baseline attributes. Using peer-reviewed literature, the research team has identified confounding variables that models will be adjusted for. These covariates include patient gender, age, race, education, and health status.

Qualitative data related to secondary outcomes will be transcribed, de-identified, and analyzed

based on qualitative description. A HIPPA-compatible, professional transcription service will be used for interview transcription. NVivo software will be used for qualitative analyses. A codebook will be determined by a three-person team with a single coder then analyzing the transcripts. Line-by-line, axial, and theoretical consensus coding will be used to organize and summarize findings, which will be validated through triangulation, member checking, and search for disconfirming data.

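### Sections 12.4.2 and 12.5.2 name neither the baseline score nor study site as model terms, so precision available from data already collected is left unsecured

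*Combined protocol and SAP*

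**What the plan says.** Section 12.4.2 plans two kinds of analysis for quality of life. One is a simple two-group test at each visit. The other is an adjusted model, "a linear mixed model that accounts for within-subject variations due to repeated measures". It does not say which of them is the confirmatory test at 3 months. Sections 12.6.2 and 12.6.3 size the trial on the unpaired t-test.

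On covariates, 12.4.2 says "These covariates include patient gender, age, race, education, and health status", and 12.5.2 repeats the list for the secondary outcomes. Both sections also say that the team will identify further confounders, baseline attributes among them, so the list is not closed. Site enters 12.4.2 only here: "Sensitivity analyses will assess whether there are differential effects on contingent on patient or study site characteristics on the primary outcomes". Section 12.5.2 does not mention it.

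Both missing terms are available. On the primary outcome, 10.1.4 says "The outcome of quality of life will be assessed at baseline during enrollment"; on the secondary outcomes, 10.2.4 says "The secondary outcome will be assessed at baseline during enrollment". On allocation, 3.5 says "Randomization is immediately after enrollment, stratified by study site", and 12.1.1 confirms it: "Participants are stratified by study site". No other stratification factor is named.

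**The concern.** The baseline value of a quality-of-life score is usually among the strongest predictors of the later value. If it is left out of the model, the 3-month contrast is estimated less precisely than the collected data allow. The wording also leaves open what happens to the enrollment score. As a response with free arm means, as a response with constrained arm means, as a covariate, or unused, it gives different models with different precision. That choice should be fixed before unblinding.

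Site is the stratification factor and the stated reason for the 20% variance inflation in 12.6.3, yet no main model carries it.

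A timing question bears on any remedy. Sections 10.1.2, 10.1.4, 10.2.2 and 10.2.4 place the first assessment at enrollment, and section 3.5 randomises immediately after enrollment. The Study Calendar (section 9) puts the first FACIT-PaL in the column for one week before surgery, which also holds the first palliative care visit. A score taken after allocation or after that visit is not a clean baseline.

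**Working it through.** **Inputs from 12.6.2 and 12.6.3:** standardised effect 0.40, two-sided alpha 0.05, 90% power, inflation 1.2, completion 0.86, four sites.

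**Assumed, because the documents do not give them:** baseline-to-3-month correlation ρ of 0.3, 0.5 or 0.7; share R² of both scores explained by the five listed covariates, 10% or 20%, through the same linear predictor; equal site sizes; share of patients without a valid baseline.

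**The plan's own figure.** The t-test needs 132.3, so 133 per arm. 133 × 1.2 / 0.86 = 185.6, which gives 186 per arm. The figure reproduces. In reverse, 186 × 0.86 = 160 completers per arm, and 160 / 1.2 = 133 effective patients per arm. Unadjusted power is 90.15% at 133 and 94.60% at 160.

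**Gain over the planned five-covariate model.** The partial correlation of baseline with outcome is (ρ − R²)/(1 − R²). Residual variance is v = 1 − R² with the covariates alone, and v = (1 − R²)(1 − partial²) with baseline added. Power is that of a t-test with effect 0.40/√v. For example, at R² = 0.10 and ρ = 0.5 the partial correlation is 0.40/0.90 = 0.444 and v = 0.90 × (1 − 0.1975) = 0.722.

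| Per arm | R² | Covariates only | Adding baseline, ρ = 0.3 / 0.5 / 0.7 | Gain in points |
|---|---|---|---|---|
| 160 | 0.10 | 96.41% | 97.10 / 98.74 / 99.90% | 0.7 / 2.3 / 3.5 |
| 160 | 0.20 | 97.87% | 98.03 / 99.04 / 99.92% | 0.2 / 1.2 / 2.1 |
| 133 | 0.10 | 92.87% | 93.99 / 96.89 / 99.58% | 1.1 / 4.0 / 6.7 |
| 133 | 0.20 | 95.29% | 95.57 / 97.50 / 99.65% | 0.3 / 2.2 / 4.4 |

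**Upper bound.** Against a wholly unadjusted test at 133 per arm, v = 1 − ρ² gives 92.60%, 96.35% and 99.52%, which is 2.5, 6.2 and 9.4 points above 90.15%.

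**Missing baselines (133 per arm, no other covariates).** Dropping a share m of patients multiplies the variance by 1/(1 − m), and baseline multiplies it by 1 − ρ². A covariate model that drops patients therefore loses to the unadjusted test once m exceeds ρ²: 9%, 25% or 49%. At an assumed m of 20%, dropping them gives 86.1%, 91.8% and 98.2%. Baseline as a response with equal arm means gives 92.2%, 95.5% and 99.1%.

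**Site.** Reading the 20% inflation as 1 + (patients per site − 1) × ICC, with 372/4 = 93 patients per site, the implied ICC is 0.2/92 = 0.0022. With four equal sites, ignoring site multiplies the SE by √[(1 − ICC + 0.75 ICC)/(1 − ICC)]. That widens it by about 0.1% at the implied ICC, and by 0.8%, 2.0% and 4.1% at assumed ICCs of 0.02, 0.05 and 0.10.

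**The case against.** The list is introduced as inclusive and refers to baseline attributes, so nothing forbids either term. Enrollment is also one of the five scheduled quality-of-life assessments, so the enrollment score may already be meant as a response row in the mixed model. Both points stand, and they are why the gain is called unsecured. They do not close the gap: with arm means left free at baseline, the 3-month contrast gains little, and the text states no constraint.

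A second objection also stands. If the t-test used for sizing is the primary test, new terms in the mixed model do nothing for its power. The remedy must therefore name the primary test.

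Third, patients are individually randomised within sites, so charging the full 20% inflation overstates the scope for gain. The 160-per-arm rows deserve the most weight.

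Section 12.4.1 says "all data from study patients in both intervention and control arms are used", but its qualifier concerns adherence to the assigned arm, not missing baselines. It supports keeping every patient in spirit; it does not dictate a method.

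A reader might infer that the trial is underpowered or its test invalid. The documents do not support that: the sample size reproduces without any adjustment, and under stratified randomisation ignoring site makes the test slightly conservative. Nor can the 2.5, 6.2 and 9.4 points be read as the expected gain, because the planned model already adjusts for five covariates.

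**Conclusion.** The concern holds as a gap in pre-specification and efficiency. It is not an error in sample size or validity. Over the planned covariate model, naming baseline FACIT-PaL is worth roughly 0.2 to 3.5 power points at 160 completers per arm, or 0.3 to 6.7 points if the inflation is kept. These sizes rest on the assumed correlations and covariate R², and on every patient having a usable baseline. If many first scores turn out to follow randomisation, the gain shrinks. Site adds next to nothing at the ICC implied by 12.6.3; its case is consistency with the design. The omission itself is certain from the text, but the size of the gain is not. The change is worth making because it costs almost nothing and removes a modelling choice that would otherwise be made later.

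**What to change.** In 12.4.2:

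- State that the primary test is the arm contrast at 3 months from the linear mixed model with arm-by-visit terms, and that the visit-wise t-tests are supportive.
- Add study site as a fixed effect with four levels.
- Add baseline FACIT-PaL, either as a response with arm means constrained equal at baseline, or as a covariate with missing baselines filled by the mean pooled over arms. Either way no patient is dropped.
- Define baseline as the score completed before randomisation.

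Reconcile the Study Calendar with 10.1.2, 10.1.4, 10.2.2 and 10.2.4 on when the first assessment takes place. In 12.5.2, make the same additions for each repeated secondary outcome with a baseline score: ESAS, FACIT-Sp-12, PROMIS-29 and the caregiver ZBI-12.

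The cost is SAP wording before unblinding, three degrees of freedom for site and a few for baseline, and a check of first-survey dates against randomisation. No new data collection is needed.

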# **3. PARTICIPANT SELECTION AND ENROLLMENT PROCEDURES**

## **3.1 Inclusion Criteria**

- 3.1.1 Patient is pursuing non-emergent, upper gastrointestinal cancer-related surgery with a goal of primary resection of the tumor – optimal surgical goal is cure, not merely disease palliation.
- 3.1.2 Eligible cancers for this study include pancreatic, hepatocellular, esophageal, gastric, and/or cholangio-carcinomas.
- 3.1.3 Must have no previous involvement of specialist palliative care providers in their care course.
- 3.1.4 Potential study patients must be able to give informed consent and be at least 18 years of age. As assessment for capacity for informed consent is a standard part of the surgical consent process, no patient is referred for the study without having been seen by the surgeon and deemed competent per the surgical team standard protocols.
- 3.1.5 No ECOG or Karnofsky Performance Status will be utilized.
- 3.1.6 One caregiver per patient is also asked to participate. In addition to being identified by the patient as being a key caregiver throughout the surgery period, these caregivers must also be able to give informed consent and be at least 18 years of age.
- 3.1.7 Ability to understand and the willingness to sign a written informed consent document.

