## **3.2 Exclusion Criteria**

- 3.2.1 Previous involvement of palliative care providers in patient's care course.
- 3.2.2 Not having one of the eligible cancers: Pancreatic, hepatocellular, esophageal, gastric, or cholangio-carcinoma.
- 3.2.3 Pursuit of emergent surgery for the upper gastrointestinal cancer.
- 3.2.4 No exclusion requirements due to co-morbid disease or incurrent illness.
- 3.2.5 Pregnant or nursing patients will not be excluded from the study.

3.2.6 Patients who are cancer survivors or those who are HIV-positive will be not excluded from the study.

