### **3.4 Registration Process**

A trained research coordinator obtains consent. The research coordinator is familiar with all aspects of the study. Consent is obtained either in-person at Stanford Hospital or clinics after the research coordinator approaches potential patients about the study or via telephone after the study has been introduced by the patient's surgical oncologist. As much time as necessary is devoted to consent discussion, with ample time for patients or caregivers to ask any questions. If participants are unsure about their participation, they have the opportunity to contact the study team prior to their surgery. To minimize the possibility of coercion, the research coordinator emphasizes that participation is completely voluntary and that patients or caregivers are not required to participate in the study. During the consenting process, the research coordinator questions the patient or caregiver to verify that they understand the purpose and summary of the study as what would be required of them; if participants do not understand English or have a hearing impairment, we use translators in the consent process.

To register the subject, the study site utilizes the central Stanford study REDcap database. The individual enters all subject eligibility and consent information. No subject begins treatment prior to registration and assignment of a subject identification number.

At registration, each study site coordinator assigns eligible subject an identification number. This identification number is used on the shared Stanford REDcap database as the record indicator. The subject's identification number is used on all subject-specific Case Report Forms (CRFs) and serious adverse event (SAE) forms. Participant information is entered into Oncore within 7 days.

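### Cancer type is not pre-specified as a covariate in the adjusted models, although five cancers are pooled and randomisation is stratified by site only

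*Combined protocol and SAP*

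**What the plan says.** Section 3.1 sets the case mix: "Eligible cancers for this study include pancreatic, hepatocellular, esophageal, gastric, and/or cholangio-carcinomas". Section 3.2 makes the diagnosis an exclusion item: "Not having one of the eligible cancers: Pancreatic, hepatocellular, esophageal, gastric, or cholangio-carcinoma". On what is captured at registration in the central database, section 3.4 says: "The individual enters all subject eligibility and consent information".

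On allocation, section 3.5 says: "Randomization is immediately after enrollment, stratified by study site, and completed via computer-generated random allocation with a block size of 6". Section 12.1.1 repeats this and adds no other stratification factor.

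On adjustment, section 12.4.2 has two statements. The first is open: "For all models, the research team will identify possible confounding variables for model adjustment, including baseline attributes". The second says the set has already been chosen from the literature and lists it: "These covariates include patient gender, age, race, education, and health status". Section 12.5.2 repeats both for the secondary outcomes. The nearest other provision in 12.4.2 is: "Sensitivity analyses will assess whether there are differential effects on contingent on patient or study site characteristics on the primary outcomes". No section provides for adjusting or stratifying by cancer type.

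**The concern.** Cancer type is fixed before randomisation and must be known for every patient. It is also a plausible prognostic factor. By their titles, several of the protocol's own references on surgical outcome deal with a particular organ or operation (esophageal cancer, pancreatectomy, hepato-pancreato-biliary surgery, pancreatoduodenectomy). Yet it enters neither the allocation scheme nor the named covariates, while general demographic variables do.

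Two things are at stake. One is precision: variance that cancer type could explain stays in the residual, and a chance difference in case mix between arms goes unadjusted. The other is pre-specification. Section 12.3 plans significance tests of baseline differences between arms, and section 12.4.2 leaves the covariate list open with no closing date. Cancer type could therefore be added or left out after its imbalance has been seen.

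**Working it through.** **Inputs from the documents** (12.6.2, 12.6.3): effect 0.4 SD, two-sided alpha 0.05, 90% power, two-sample t-test without covariates, completion 0.86, variance inflation 1.20, 186 per arm, goal 380.

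**Assumed, because the documents do not give them:** the share of residual variance that cancer type explains (R2, 0.02 to 0.10), the share of patients with a given cancer (10% to 40%), and the outcome difference between that cancer and the rest (0.3 to 0.5 SD).

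**1. The plan's own figure.** The normal approximation gives 2 × (1.960 + 1.282)² / 0.4² = 131.3, so 132 per arm; 132 × 1.20 / 0.86 = 184.2, so 185. The exact t-test gives 132.3, so 133; 133 × 1.20 = 159.6, so 160; 160 / 0.86 = 186.05. The stated 186 is reproduced. It uses no covariates, so omitting cancer type does not make it wrong.

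**2. Precision.** The effective number per arm is 186 × 0.86 / 1.20 = 133.3. Power = Φ(0.4 / √(2(1 − R2) / 133.3) − 1.96). This carries the plan's t-test calculation over to a smaller residual variance; it is not a full mixed-model calculation.

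| Assumed R2 | Power at 186 per arm | Required n per arm |
|---|---|---|
| 0 | 90.4% | 185 |
| 0.02 | 91.0% | 180 |
| 0.05 | 91.8% | 175 |
| 0.10 | 93.1% | 167 |

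**3. Chance imbalance.** Expected completers per arm are 190 × 0.86 = 163. The 95% range for the between-arm difference in one cancer's share p is ±1.96 × √(2p(1 − p) / 163). The shift in the unadjusted estimate at the edge of that range is the imbalance times the assumed outcome difference.

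| Assumed share | 95% range | Shift at 0.3 SD | Shift at 0.5 SD |
|---|---|---|---|
| 10% | ±6.5 points | 0.020 SD | 0.033 SD |
| 20% | ±8.7 points | 0.026 SD | 0.043 SD |
| 40% | ±10.6 points | 0.032 SD | 0.053 SD |

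For scale, the standard error of the unadjusted effect is √(2 / 163) = 0.11 SD, so the largest shift shown is just under half of one standard error (0.053 / 0.11 = 0.48).

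**4. Steps 2 and 3 are largely one quantity.** A cancer with a 40% share and a 0.4 SD difference accounts for 0.4 × 0.6 × 0.4² = 0.038 of the variance, which lies inside the R2 range of step 2. The two sizes should not be added.

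**5. Deaths.** Section 12.6.3 assumes 3% mortality at 12 weeks: 0.03 × 380 = 11.4, or about 11 deaths. Six-month mortality is not given.

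**The case against.** **The list is not closed.** It is introduced as inclusive, and baseline attributes may still be added, so a reader who infers that the plan excludes cancer type goes too far. That stands. But permission to add a covariate is not a commitment to do so, and it leaves the choice open. Blinding of the principal investigator and analysts (3.5) reduces that risk without replacing pre-specification.

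**Other text may already cover it.** Health status is undefined, and 12.3 ties health status measures to chart abstraction, but nothing says these include diagnosis. The sensitivity analysis in 12.4.2 concerns effect modification by unnamed characteristics, which is not adjustment. Site stratification could help only indirectly, through differences in case mix between sites.

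**Randomisation already deals with it.** A reader might infer that the design fails to balance cancer type and that the result is biased. The documents do not support this. Random allocation balances cancer type in expectation, and the confidence interval of the unadjusted comparison already allows for chance imbalance.

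**The size is small and assumed.** This stands. A reader might also take cancer type to be the main source of variation in recovery, but no section reports quality of life, recovery or risk by diagnosis. The 0.02 to 0.05 SD figures are for the edge of the 95% range and for an unadjusted estimate; the listed covariates may already absorb part of the shift.

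**Choosing covariates is partly judgement.** The plan says its set came from peer-reviewed literature, which cannot be checked here. That is a fair reason to treat this as an improvement and not an error.

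**Conclusion.** The point holds as a modest, inexpensive improvement. Cancer type is a pre-randomisation factor that the trial very likely already holds, and neither the allocation scheme nor the named covariates use it. That diagnosis is stored as its own field is inferred from sections 3.1, 3.2 and 3.4, not stated.

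On an assumed R2 of 0.02 to 0.10, adjustment adds about 0.6 to 2.7 percentage points of power (90.4% to between 91.0% and 93.1%). Seen as chance imbalance, largely the same benefit is a shift of about 0.02 to 0.05 SD at the edge of the 95% range, on assumed shares of 10% to 40% and differences of 0.3 to 0.5 SD. The gain that needs no assumption is that the covariate choice is closed in advance. The validity of the randomised comparison and the sample size justification are not in question.

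**What to change.** Before unblinding, amend 12.4.2 and 12.5.2 so that cancer type is a named fixed factor in the linear mixed models for patient outcomes. State with it:

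- a rule for pooling sparse diagnoses, set on counts combined over both arms;
- a rule for patients with more than one eligible diagnosis, which the and/or wording in 3.1 allows, for example the diagnosis for which resection was planned at enrollment;
- that the covariate list is then final.

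Do not carry the factor into the mortality Cox model as a multi-parameter term unless the number of deaths supports it. With about 11 deaths expected by 12 weeks, four more parameters beside the existing covariates could make that model unstable.

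Stratifying now is not a practical alternative, since 12.6.1 reports 381 enrolled by March 31, 2022 against a goal of 380. The unadjusted per-visit tests in 12.4.2 are unaffected by this change.

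The cost is at most 4 degrees of freedom against about 327 expected completers (380 × 0.86 = 326.8). No new data collection should be needed, subject to confirming that diagnosis is held as a field.
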